7.4.3.1 Demographics

The following demographic covariates will be assessed in the mother's record on cohort entry date (or for Optum's Market Clarity Data, the nearest visit to the cohort entry date):

- Age
- Calendar year
- Geographic region (Northeast, West, Midwest, South, unknown)

7.4.3.2 Healthcare Utilization

Healthcare utilization will be assessed using data available up to 1 year prior to cohort entry unless otherwise noted.

- Duration of continuous health plan enrollment before cohort entry (assessed in claims databases only using all available data prior to cohort entry, up to 5 years)
- Number of outpatient visits
- Number of emergency department visits
- Number of hospitalizations

7.4.3.3 Comorbidities

All comorbidities will be assessed using diagnosis and procedure codes using all available data prior to cohort entry (up to 5 years).

- Allergic conjunctivitis ([Thyssen et al., 2023](#))
- Allergic contact dermatitis ([Thyssen et al., 2023](#))
- Allergic rhinitis ([Thyssen et al., 2023](#))
- Alopecia areata ([Thyssen et al., 2023](#))

- Anxiety (Huang et al., 2020b; Thyssen et al., 2023)
- Asthma (Thyssen et al., 2023)
- Attention-deficit/hyperactivity disorder (Thyssen et al., 2023)
- Depression (Huang et al., 2020b; Thyssen et al., 2023)
- Diabetes (Huang et al., 2020b)
- Eosinophilic esophagitis (Thyssen et al., 2023)
- Food allergies (Thyssen et al., 2023)
- HIV (Huang et al., 2020b)
- Hyperlipidemia (Huang et al., 2020b)
- Hypertension (Huang et al., 2020b; Thyssen et al., 2023)
- Inflammatory bowel disease (Thyssen et al., 2023)
- Obesity (Thyssen et al., 2023)
- Psoriasis (Huang et al., 2020b)
- Rheumatoid arthritis (Thyssen et al., 2023)
- Vitiligo (Thyssen et al., 2023)

7.4.3.4 Pregnancy History and Risk Factors

Pregnancy history and risk factors will be assessed using diagnosis and procedure codes using all available data prior to cohort entry (up to 5 years).

- Gravidity, the number of pregnancies before the current pregnancy
- Parity, the number of vaginal deliveries or C-sections before the current pregnancy
- History of pregnancy complications
 - Spontaneous abortions
 - Elective terminations
 - Ectopic pregnancies
 - Preterm births
 - Stillbirths
 - Gestational hypertension
 - Gestational diabetes
 - Pre-eclampsia
 - Eclampsia
- Chronic kidney disease
- Other cardiovascular disease

- History of infertility
- Tobacco use
- Alcohol and drug-related diagnoses
- Maternal Comorbidity Score ([Bateman et al., 2013](#))

7.4.3.5 AD and PN History and Treatment

Covariates related to AD and PN history and treatment will be using all available data prior to the cohort entry (up to 5 years). The AD therapies include treatments that are for mild AD and are not included in the moderate to severe AD algorithm.

- AD
 - Number of AD diagnoses on unique days
- PN
 - Number of PN diagnoses on unique days
- Treatments for AD and/or PN
 - Abrocitinib
 - Dupilumab
 - Lebrikizumab
 - Tralokinumab
 - Upadacitinib
 - Baricitinib
 - Topical Tacrolimus
 - Crisaborole
 - Oral and parental corticosteroids
 - Phototherapy
 - Systemic immunosuppressants
 - Cyclosporine
 - Azathioprine
 - Methotrexate
 - Mycophenolate
 - Belimumab
 - Leflunomide
 - Interferon gamma
 - Rituximab

- Topical corticosteroids
 - High potency
 - Medium potency
 - Low potency
- Topical calcineurin inhibitors
- Topical tacrolimus, pimecrolimus
- Gabapentinoids (gabapentin, pregabalin)
- Cannabinoids
- Antidepressants (serotonin and norepinephrine reuptake inhibitors, selective serotonin reuptake inhibitors, or tricyclic antidepressants)
- Topical ketamine/amitriptyline/lidocaine
- Topical calcipotriol

7.4.3.6 Characteristics of Current Pregnancy

The following covariates will be assessed during the current pregnancy (ECD through end of pregnancy) and included in descriptive analyses only (not in propensity score models):

- Number and frequency of prenatal care visits
- Prenatal and delivery care markers (e.g., amniocentesis, ultrasound, antenatal screening)
- Receipt of Tdap vaccine
- Tobacco use
- Alcohol use
- Multiple pregnancy vs. singleton pregnancy
- Exposure to teratogens
- TORCH infections during pregnancy
- SARS-CoV-2 infection during pregnancy

7.4.3.7 Infant Covariates

Infant covariates will be assessed during the first year of life and included in descriptive analyses only (not in propensity score models):

- Sex
- Multiple birth vs singleton birth
- Duration of continuous medical and pharmacy coverage (in claims databases only)

7.5 Study Size

Table 3 presents the minimum number of nemolizumab exposed pregnancies required to detect relative risks equal to or greater than 2.0, 2.5, or 3.0 for a comparative analysis of each of the study outcomes, assuming a ratio of 1:4 exposed to unexposed, 80% power, a 2-sided alpha of 0.05, and the referenced outcome prevalences. For infant outcomes, the minimum number of nemolizumab-exposed livebirths was calculated, and the number of nemolizumab-exposed pregnancies was derived from these counts based on the prevalence of live birth. For the primary outcome MCM, a study size of 214 live births with linked infants exposed to nemolizumab in the first trimester exposure window would provide an 80% power to detect a RR of 2.5, and 133 live births with linked infants exposed to nemolizumab in the first trimester exposure window would provide 80% power to detect a RR of 3. Assuming 80% of pregnancies have an observed outcome and 76% of observed outcomes are live births, an estimated 352 pregnancies exposed to nemolizumab during the first trimester would need to be accrued to detect a RR of 2.5 and 219 exposed pregnancies to detect a RR of 3. With a 1:4 ratio of exposed to unexposed, this corresponds to 1,408 pregnancies (for 2.5) or 876 (for 3) in each comparator group.

Table 3 Sample size required for 80% power to detect effect estimates for pregnancy and infant outcomes, with 1:4 matching¹

Outcome	Prevalence of Outcome	Relative Risk	Nemolizumab Exposed Pregnancies Needed	Nemolizumab Exposed Live Births Needed
MCM	3% ²	2	709	431
		2.5	352	214
		3	219	133
Ectopic pregnancy	1-2%	2	877	N/A
		2.5	438	
		3	275	
Elective termination	21%	2	45	N/A
		2.5	21	
		3	12	
Preterm birth, SGA birth	10% ^{3,4}	2	190	115
		2.5	94	57
		3	56	34
Spontaneous abortion	14% ⁵	2	77	N/A
		2.5	37	
		3	22	
Stillbirth	1% ⁶	2	1,324	N/A
		2.5	662	
		3	415	

Abbreviations: N/A, not applicable; SGA, small for gestational age

¹ Calculations were performed via www.OpenEpi.com using the Fleiss method, as described in Fleiss JL. Statistical Methods for Rates and Proportions. John Wiley & Sons, 1981.

² March of Dimes. Perinatal Data Snapshot: United States Birth Defects. 2015; http://www.marchofdimes.org/peristats/pdflib/999/pds_99_4.pdf.

³ Centers for Disease Control and Prevention. Quick Stats: Percentage of Small for gestational-Age Births, by Race and Hispanic Ethnicity—United States, 2005. MMWR. 2008;57(50):1359. <https://www.cdc.gov/mmwr/preview/mmwrhtml/mm5750a5.htm>.

⁴ National Vital Statistics Reports. Birth: Final Data for 2021. Volume 72, Number 1 (January 31, 2023). <https://www.cdc.gov/nchs/data/nvsr/nvsr72/nvsr72-01.pdf>.

⁵ Yadava B. Jeve and William Davies. Evidence-based management of recurrent miscarriages. J Hum Reprod Sci. 2014 Jul-Sep; 7(3): 159–169.

⁶ Food and Drug Administration. Guidance for Industry: Establishing Pregnancy Exposure Registries. United States Department of Health and Human Services, ed. Rockville, MD 2002.

Table 4 shows counts of pregnancies with at least 1 diagnosis code for AD or PN by year in the ORD. These counts are for informational purposes only. The sample size for the final study could increase or decrease depending on actual uptake and criteria applied during the conduct of the protocol.

Table 4 Counts of pregnancies in the Optum Research Database with an AD or PN diagnosis code and a dispensing of dupilumab, 2020-2024

	2020	2021	2022	2023	2024*	Total
Pregnancies with an AD code	1,474	1,608	1,731	1,716	735	7,264
Dupilumab dispensing	38	44	48	55	24	209
Pregnancies with a PN code	26	59	52	58	12	207
Dupilumab dispensing	0	0	0	2	0	2

Abbreviations: AD, atopic dermatitis; PN, prurigo nodularis

* This indicates an incomplete year.

The PSURs will describe accrual of nemolizumab-exposed pregnancies and the feasibility of meeting the target study size. Additional data sources will be added after the feasibility report is conducted as part of 2029 PSUR.

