Stillbirth	Entire pregnancy	Week 2 – Week 40	Later of cohort entry or 20 weeks + 0 days	End of pregnancy, disenrollment from the health plan/8 weeks of no clinical activity, or the end of the study period
MCM	First trimester	Week 2 – Week 13	Delivery	First year of life, disenrollment from the health plan/8 weeks of no clinical activity, or the end of the study period
SGA birth	Entire pregnancy	Week 2 – Week 40	Delivery	First year of life, disenrollment from the health plan/8 weeks of no clinical activity, or the end of the study period

Abbreviations: ECD, estimated conception date; EHR, electronic health record; MCM, major congenital malformation; SGA, small for gestational age

¹ For individuals with a cohort entry date after the pre-specified start of follow-up, follow-up begins at cohort entry. For example, for cohorts beginning at 24 gestational weeks, follow-up for stillbirth will begin at 24 gestational weeks.

² For EHR and linked claims-EHR data sources, pregnancies will be censored at the end of 8 weeks of no clinical activity. Since pregnant women should regularly interact with the healthcare system, this censoring criterion will indicate loss to follow-up in the database.

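### Table 3: the exposed-pregnancy figures for ectopic pregnancy, elective termination, spontaneous abortion and stillbirth omit the plan's 80% observed-outcome allowance, and the ectopic row rests on an unstated 1.5%

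*Protocol*

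**What the plan says.** Protocol section 7.5 introduces Table 3 as the minimum number of exposed pregnancies "required to detect relative risks equal to or greater than 2.0, 2.5, or 3.0", "assuming a ratio of 1:4 exposed to unexposed, 80% power, a 2-sided alpha of 0.05, and the referenced outcome prevalences". The table title repeats the claim: "Sample size required for 80% power to detect effect estimates for pregnancy and infant outcomes, with 1:4 matching". The method is given in a footnote: "Calculations were performed via www.OpenEpi.com using the Fleiss method".

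A conversion from live births to pregnancies is described for one group of rows: "For infant outcomes, the minimum number of nemolizumab-exposed livebirths was calculated, and the number of nemolizumab-exposed pregnancies was derived from these counts". The factors appear in the MCM derivation: "Assuming 80% of pregnancies have an observed outcome and 76% of observed outcomes are live births".

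For the other four outcomes the live-birth column is marked not applicable and only the pregnancy column is filled, for example "Ectopic pregnancy 1-2% 2 877 N/A". In Table 2 (section 7.3.6.2), stillbirth follow-up begins at the "Later of cohort entry or 20 weeks + 0 days".

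**The concern.** One column, under one heading, appears to hold two quantities. In the MCM and preterm/SGA rows it holds pregnancies to accrue, after allowing for unobserved outcomes and for pregnancies that do not end in live birth. In the other four rows it seems to hold pregnancies with an observed outcome. If so, accruing the printed number does not deliver the stated 80% power for those four outcomes.

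The ectopic row raises a second question, because a single sample size is printed against a prevalence range that spans a factor of two.

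At stake is the accuracy of a stated sample size and power. The rows that matter most are ectopic pregnancy and stillbirth, whose requirements are large relative to the 352 exposed pregnancies planned for MCM.

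**Working it through.** **Inputs (section 7.5).** Two-sided alpha 0.05, power 80%, r = 4 comparators per exposed pregnancy, RR 2 / 2.5 / 3. Comparator risks p0: MCM 3%, preterm/SGA 10%, elective termination 21%, spontaneous abortion 14%, stillbirth 1%, ectopic 1-2%. Observed share 0.80; live births among observed outcomes 0.76.

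**Formula.** Fleiss, without continuity correction, with p1 = RR x p0 and pbar = (p1 + r p0)/(r + 1):

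n = [1.96 sqrt((r+1) pbar(1-pbar)) + 0.8416 sqrt(r p1(1-p1) + p0(1-p0))]^2 / [r (p1-p0)^2]

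Example, stillbirth at RR 2: p1 = 0.02, pbar = 0.012; n = (0.4772 + 0.2501)^2 / 0.0004, about 1,322. The table prints 1,324. With continuity correction n would be 1,445, so the uncorrected form was used.

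**Step 1. Reproduce the converted rows.** MCM Fleiss n is 427.9 / 213.3 / 132.6 against printed live births of 431 / 214 / 133. The small gap at RR 2 is immaterial here. Dividing the printed live births by 0.80 x 0.76 = 0.608 gives 709 / 352 / 219, as printed. For preterm/SGA, 115/0.608 = 189 (printed 190), 57/0.608 = 94 and 34/0.608 = 56.

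**Step 2. Reproduce the other four rows.**

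| Outcome (p0) | Fleiss n, RR 2 / 2.5 / 3 | Printed exposed pregnancies |
|---|---|---|
| Ectopic (1.5%) | 875 / 438 / 273 | 877 / 438 / 275 |
| Elective termination (21%) | 44.5 / 20.6 / 11.7 | 45 / 21 / 12 |
| Spontaneous abortion (14%) | 76.5 / 36.7 / 21.9 | 77 / 37 / 22 |
| Stillbirth (1%) | 1,322 / 663 / 414 | 1,324 / 662 / 415 |

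The printed figures are the unconverted n, so no 0.80 factor was applied.

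**Step 3. Power if 80% of the printed number is observed** (same share in both arms, unobserved pregnancies contributing nothing), and printed n divided by 0.80:

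| Outcome | Power, RR 2 / 2.5 / 3 | Printed n / 0.80, rounded up |
|---|---|---|
| Ectopic (1.5%) | 72.1 / 72.3 / 72.8% | 1,097 / 548 / 344 |
| Elective termination | 71.8 / 72.0 / 71.8% | 57 / 27 / 15 |
| Spontaneous abortion | 71.9 / 72.1 / 72.0% | 97 / 47 / 28 |
| Stillbirth | 72.1 / 72.3 / 72.6% | 1,655 / 828 / 519 |

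**Step 4. Ectopic row across its stated range** (printed 877 / 438 / 275):

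| p0 | Fleiss n | Power at printed n | Power at 0.80 x printed n |
|---|---|---|---|
| 1% | 1,322 / 663 / 414 | 65.1 / 65.6 / 66.2% | 57.0 / 57.9 / 58.7% |
| 2% | 652 / 326 / 203 | 89.2 / 88.9 / 88.9% | 82.5 / 82.4 / 82.5% |

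The 1% line is the stillbirth row of the same table, which confirms that 877 is not a 1% figure.

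**Step 5. Stillbirth denominator.** Section 7.5 does not say whether the 1% is per pregnancy or per pregnancy reaching 20 weeks. Assume that 77% of observed pregnancies reach 20 weeks (76% live births + 1%).
- Per pregnancy reaching 20 weeks: the usable share is 0.80 x 0.77 = 0.616. The printed n then has 62.4 / 63.1 / 63.7% power, and the requirement is 1,324/0.616 = 2,150, 662/0.616 = 1,075 and 415/0.616 = 674.
- Per pregnancy: the risk among those reaching 20 weeks is 0.01/0.77 = 1.30%. Fleiss n at 1.30% divided by 0.77 is 1,317 / 659 / 412, almost the printed figures. The 20-week restriction cancels, and with the 0.80 factor power is 72 to 73%.

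**The case against.** **The conversion was meant for infant outcomes only, and the 80% is stated only for MCM.** This describes the inconsistency without justifying it. The 80% is stated as a share of pregnancies, not of infants. Preterm birth is listed as a pregnancy outcome (section 7.4.2.1.4), yet its row carries the full conversion.

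**The four outcomes are analysed with Cox models (section 7.7.3.3), which use follow-up before censoring.** This stands in part. Spontaneous abortion and elective termination are censored at 20 weeks, and ectopic pregnancy is an early event, so a pregnancy lost later can be fully informative for them. If 90% or 95% of pregnancies are informative, power at RR 2 is about 76% or 78%. The 72% is therefore a floor. Table 3 itself takes no such credit: it uses a two-proportion method, and preterm birth, also analysed by Cox, was converted.

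**1.5% is simply the midpoint of 1-2%.** That is probably how it arose, but it is not stated, and the row supports 80% power over only part of its printed range.

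**Nothing turns on it.** Largely fair for the study target, which is set by MCM. Dividing by 0.80 moves no cell past 352, and the table as printed already shows 352 to be too few for stillbirth at every RR and for ectopic pregnancy at RR 2 and 2.5. There are also no a priori hypotheses (section 6).

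**A stronger reading to avoid.** A reader might infer from the 20-week start of follow-up that stillbirth power is only about 62%. The missing 0.80 factor does not produce that figure. It also needs the 1% to be a rate among pregnancies reaching 20 weeks, which section 7.5 does not say. If the 1% is per pregnancy, power stays near 72%.

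**Conclusion.** The point holds as an error in a stated sample size. Four of the six rows of Table 3 report unconverted Fleiss numbers under a heading that means pregnancies to accrue. With the plan's 80% observed share they give 71.8% to 72.8% power in all 12 cells if unobserved pregnancies add nothing, and between 72% and 80% otherwise, with the smallest shortfall likely for the early outcomes.

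The ectopic row is separately mislabelled. With the 0.80 factor, its power at RR 2 runs from about 57% to 82% over the stated prevalence range. The adverse end should not be cited without the favourable one.

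For elective termination and spontaneous abortion the change is of no practical consequence, since the corrected figures are at most 57 and 97. For ectopic pregnancy and stillbirth the printed requirement is about a fifth below the converted one. The MCM figures, including the 352 target, are correct and unaffected. The results assume equal loss in both arms and the two-proportion method that the plan itself uses.

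**What to change.** In Table 3, do one of the following for ectopic pregnancy, elective termination, spontaneous abortion and stillbirth:
- divide by 0.80, giving 1,097 / 548 / 344 (ectopic at 1.5%), 57 / 27 / 15, 97 / 47 / 28 and 1,655 / 828 / 519; or
- keep the printed numbers and label them as pregnancies with an observed outcome.

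Label the ectopic row 1.5%, or show it at both 1% and 2%.

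State whether the 1% stillbirth rate is per pregnancy or per pregnancy reaching 20 weeks. Only in the latter case divide further by the share reaching 20 weeks. At an assumed 77% that gives about 2,150 / 1,075 / 674.

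The cost is a corrected table or footnote at the next protocol amendment. The target, design and data collection do not change.

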Data sources: The patients included in this study will be drawn from the Optum Research Database [ORD], a proprietary research database containing eligibility and pharmacy and medical claims data from a large United States (US) health plan affiliated with Optum. Within the ORD, we will identify pregnancies and employ mother-child linkages using Optum's Dynamic Assessment of Pregnancies and Infants (DAPI), a proprietary process that includes a set of capabilities and established algorithms that is applied to claims data to identify pregnancies, trimesters, and pregnancy outcomes, and to link mothers' and infants' data in an ongoing manner, within the ORD. As additional data sources will be needed to achieve an adequate sample size for the study of rare pregnancy and infant outcomes, Optum's Market Clarity Data (linked claims-electronic health record [EHR] database) and a feasibility assessment of additional potential data sources will be included in the 2029 Periodic Safety Update Report (PSUR; see [Section 4](#)).

Study size: The target size is 352 nemolizumab-exposed pregnancies and 1,408 pregnancies in each comparator group, which will provide 80% power to detect a relative risk of 2.5 for MCMs, while 219 nemolizumab-exposed pregnancies and 876 pregnancies in each comparator group will provide 80% power to detect a relative risk of 3 for MCMs.

Data analysis: The accrual of nemolizumab-exposed pregnancies and live births in the data sources will be reported in the PSURs. For the final report, this study will be conducted using a

sequential cohort design that aligns cohort entry at gestational week of drug dispensing or administration. Exposed pregnancies will be matched in a 1:4 ratio to active comparator and unexposed pregnancies based on maternal age at cohort entry, gestational week of dispensing, indication, and calendar week. We will estimate RRs using robust Poisson regression models and HRs using Cox proportional hazards models.

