7.2.1.1 Optum Dynamic Assessment of Pregnancies and Infants (DAPI)

For analyses of pregnancy and infant outcomes, the cohorts for this study will employ the mother-child linkages established using DAPI, a proprietary process that includes a set of capabilities and established algorithms applied to claims data to identify pregnancies, trimesters, and pregnancy outcomes, and to link mothers' and infants' data in an ongoing manner within the ORD (Bertoia et al., 2022). There were approximately 170,000 new pregnancies identified in 2022 within the database. Approximately 85% of pregnancies resulting in live births can be linked to an infant. These linkages enable proactive monitoring of pregnancy outcomes to ascertain a range of outcome-specific risks associated with drug exposure during pregnancy.

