7.7.1 Annual Monitoring

Optum will tabulate counts of pregnancies exposed to nemolizumab (from 95 days [i.e., 5 times the half-life], or approximately 14 weeks, before ECD through the end of pregnancy) as well as counts of live births from these pregnancies, and the results will be included in the PSURs. Women with nemolizumab-exposed pregnancy episodes will be described according to baseline demographic and clinical characteristics (a subset of those mentioned in [Section 7.4.3](#)). Additionally, the overall number of eligible pregnancies will be tabulated and described according to the same baseline demographic and clinical characteristics. All analyses will be descriptive, including the number of observations, mean, standard deviation, median, interquartile range, and range for all continuous variables and counts and percentages for each binary or categorical variable. Counts from Optum's Market Clarity Data will be added starting with the 2029 PSUR, and additional data partners will be added based on the results of the feasibility assessment to ensure sample size projections are met (as described in [Section 7.7.2](#)).

Outcome counts (except for live births), matching, propensity score estimation, meta-analyses, and sensitivity analyses will not be performed until the final report.

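### The MCM target of 352 (or 219) exposed pregnancies leaves out mother-infant linkage; at the protocol's own 85% it gives about 75% power, not 80%

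*Protocol*

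**What the plan says.** Section 7.5 states the design inputs: "assuming a ratio of 1:4 exposed to unexposed, 80% power, a 2-sided alpha of 0.05, and the referenced outcome prevalences", calculated "using the Fleiss method" (Table 3, footnote 1), with a baseline MCM prevalence of 3%. The requirement for RR 2.5 is "a study size of 214 live births with linked infants exposed to nemolizumab in the first trimester exposure window", and for RR 3 it is "133 live births with linked infants exposed to nemolizumab in the first trimester exposure window". The step to pregnancies reads "Assuming 80% of pregnancies have an observed outcome and 76% of observed outcomes are live births, an estimated 352 pregnancies", with 219 for RR 3. The abstract repeats the result as the study's target: "The target size is 352 nemolizumab-exposed pregnancies and 1,408 pregnancies in each comparator group", said to give 80% power for RR 2.5.

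On linkage, section 7.2.1.1 says: "Approximately 85% of pregnancies resulting in live births can be linked to an infant". Section 7.2.1.1.3 says MCM and small-for-gestational-age (SGA) birth are identified from the infant's claims and not the mother's. Section 7.7.3.2 confirms that infant outcomes are restricted to pregnancies with linked infants.

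On monitoring, section 7.7.1 says: "Optum will tabulate counts of pregnancies exposed to nemolizumab". The window runs from 95 days before estimated conception to the end of pregnancy, with a count of live births alongside. Section 7.7.2 asks candidate data sources for counts by the same methods.

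**The concern.** The requirement is in linked infants, but the conversion stops at live births. It therefore treats every live birth as linked, while the protocol says that about 15% in its main database are not. The stated pairs of target and power (352 with RR 2.5, 219 with RR 3) then do not hold on the protocol's own figures.

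This matters for planning. Section 7.5 says the PSURs will describe the feasibility of meeting the target size, and data sources are to be added after the 2029 feasibility assessment. The target is low for the power claimed. The count set against it is also broader than the target: it includes exposure first occurring after the first trimester, and live births whether or not they are linked.

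**Working it through.** **Inputs.** From section 7.5: two-sided alpha 0.05, power 80%, k = 4 comparators per exposed pregnancy, p0 = 0.03, observed-outcome share 0.80, live-birth share 0.76. From section 7.2.1.1: linkage 0.85 (ORD only).

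**Reproducing the stated figures.** Fleiss formula for two proportions without continuity correction, with p̄ = (p1 + 4·p0)/5 and q = 1 − p:

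n = [1.96·√(1.25·p̄·q̄) + 0.8416·√(p1·q1 + p0·q0/4)]² / (p1 − p0)²

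- RR 2.5: p1 = 0.075, p̄ = 0.039. n = (0.4242 + 0.2330)² / 0.045² = 213.3, so 214 as stated.
- RR 3: p1 = 0.09, p̄ = 0.042. n = (0.4396 + 0.2513)² / 0.06² = 132.6, so 133 as stated.
- The continuity-corrected form gives 241 and 153, so the protocol used the uncorrected form.
- Conversion: 214/(0.80 × 0.76) = 214/0.608 = 351.97, so 352. 133/0.608 = 218.75, so 219. The two stated factors account for the whole conversion, with no room left for linkage.

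**What the targets deliver at 85% linkage.** Power = Φ{[(p1 − p0)·√n − 1.96·√(1.25·p̄·q̄)] / √(p1·q1 + p0·q0/4)}, with the comparator group kept at four times the exposed.

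- RR 2.5: 352 × 0.608 × 0.85 = 181.9 linked infants. Power = Φ{(0.6069 − 0.4242)/0.2769} = Φ(0.66) = 74.5%. Power reaches 80% only at an RR of about 2.65.
- RR 3: 219 × 0.608 × 0.85 = 113.2 linked infants; power 74.7%.

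**Targets that restore 80% power, and the range over linkage.** Pregnancies = 214 (or 133) / (0.608 × linkage), rounded up.

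| Linkage | Power of 352 at RR 2.5 | Needed for RR 2.5 (exposed / per comparator) | Needed for RR 3 (exposed / per comparator) |
|---|---|---|---|
| 100% (implicit in the plan) | 80.1% | 352 / 1,408 | 219 / 876 |
| 95% | 78.4% | 371 / 1,484 | 231 / 924 |
| 90% | 76.5% | 392 / 1,568 | 244 / 976 |
| 85% (ORD) | 74.5% | 415 / 1,660 | 258 / 1,032 |

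Only the 85% comes from the protocol; 90% and 95% are illustrative.

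**SGA row.** Table 3 uses the same 0.608 here (115/0.608 = 189.1, so 190). At 85% linkage the SGA pregnancy counts become 115/0.5168 = 223, 57/0.5168 = 111 and 34/0.5168 = 66, against 190, 94 and 56.

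**Live-birth share, as a sensitivity scenario only.** Table 3's non-live outcomes are termination 21%, spontaneous abortion 14%, ectopic 1–2% and stillbirth 1%. They sum to 37–38%. If they shared one denominator, 62–63% would remain as live births, against the 76% assumed. With 85% linkage as well, 352 × 0.80 × (0.62 to 0.63) × 0.85 = 148 to 151 linked infants, and power for RR 2.5 is 67–68%.

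**The case against.** **The 80% may already cover linkage.** The text defines it as the share of pregnancies with an observed outcome. For it to include 85% linkage, 0.80/0.85 = 94% of pregnancies would need an observed outcome, and the protocol does not say so.

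**The 85% is an ORD figure in a multi-database study.** This stands. Linkage in Market Clarity and in later sources is not stated, so 415 and 258 are one scenario and a range must be shown. It does not rescue the current calculation, which in effect assumes 100%.

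**352 is not a stopping rule.** This also stands. Accrual is set by conception dates up to 31 March 2032, all qualifying pregnancies enter, section 6 states no a priori hypotheses, and further data sources are already planned. The feasibility questionnaire asks about ability to link mothers and infants, and the final report will describe linked infants. The error therefore affects a planning claim, not the validity of the estimates. The 80% power is still stated and should be right.

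**The any-time exposure count serves the frequency objective and the whole-pregnancy outcomes.** Agreed. It should stay, with a second count beside it.

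Two stronger readings are tempting:

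- A reader might infer that Table 3 disproves the 76% share and that about 500 exposed pregnancies are needed. The documents do not establish this. The prevalences are separate planning inputs, those with references come from different sources, and nothing says they partition all pregnancies. Cohort entry for MCM runs over Weeks 2–13, so later entrants have already survived some early loss.
- A reader might infer that the ectopic, termination, spontaneous abortion and stillbirth rows must also be divided by the observed-outcome share. Those outcomes are analysed by Cox models in which censored pregnancies contribute follow-up, and entry for stillbirth runs to Week 40, so a blanket factor is not a required correction.

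**Conclusion.** The point holds for linkage. On the protocol's own 85%, the stated targets give about 75% power where 80% is claimed: a loss of about 5.5 percentage points, or a shortfall of 63 exposed pregnancies for RR 2.5 (415 − 352) and 39 for RR 3 (258 − 219). The figures rest on the protocol's 3% prevalence, full 1:4 matching and its 0.80 and 0.76. Better linkage in the added sources would shrink the gap; it closes only at 100%. The MCM exclusions in section 7.3.3.3 (teratogens, TORCH infections, chromosomal anomalies) would reduce the usable number further, but the documents give no figure and none is counted here.

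The 76% live-birth share needs an explanation beside Table 3, and the 67–68% power is a what-if, not a finding. The monitoring counts do not match the target's definition. None of this invalidates the design. It is a correction that should be made, ahead of the 2029 feasibility assessment.

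**What to change.** 1. Add an explicit linkage factor to the conversion in section 7.5, the MCM and SGA entries of Table 3, and the abstract. SGA shares a row with preterm birth, which section 7.4.2.1.4 identifies on maternal as well as infant records, so the two may need separate rows.
2. Either restate the targets (415 exposed and 1,660 per comparator for RR 2.5; 258 and 1,032 for RR 3, at 85% linkage), or keep 352 and 219 and state about 75% power. In both cases show the range over linkage, and update it once linkage in Market Clarity and the other sources is known.
3. State the source of the 76% live-birth share and reconcile it with Table 3's non-live prevalences. If they have different denominators, say so; if not, use one consistent set.
4. In the PSURs and the feasibility count request, add counts of first-trimester-exposed pregnancies and of their linked infants, and compare those with the target.

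The cost is a text and table correction plus two extra tabulations per report and data source. Design and analysis are unchanged, but the stated power becomes less favourable or the target rises by about 18% (1/0.85).
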